A minimum of 93 participants (31 participants per group) aged 4-to-13 will be recruited through convenience sampling, consented, and randomized by staff to one-of-three preparation programs (VR, mock MRI, or booklet). Details of the comparison groups are outlined in **Table 4**. Given the restricted availability of the simulator, child life specialists, and the availability of participants, we are unable to fully randomly allocate participants. As such, participants will be randomly assigned to the intervention options available according to their individual availability (using Research Randomizer <https://www.randomizer.org/>). For example, if a participant is available on a Thursday that virtual reality and booklet are available, they will be randomly allocated to one of these interventions.

This phase will have open recruitment to all children and adolescents interested in participating, such that participants may not be BCCH patients scheduled for an MRI. This recruitment strategy was selected due to the resource constraints associated with limiting the evaluation group to MRI patients only.

Table 4. Details of the comparison groups.

	VR Simulation	MRI Preparation Booklet	Mock MRI
Facilitator	Research Assistant	Research Assistant	Child Life Specialist
Location	BCCH	BCCH	Simulation Room
Content	Refer to The Virtual Reality Simulation	Refer to MRI Preparation Book	Individualized intervention in physical simulator.

The different interventions will be held in separate private rooms located in BCCH, such that the VR and booklet groups will not have prior exposure to the imaging centre or the simulation room in advance of their assessment. This is to simulate our intended delivery in hospital, medical office, or clinic settings but minimize alternative explanations associated with testing in the simulation room where assessments will take place (previously described in **Table 3**).

Data will be collected throughout the implementation process (**Figure 3**). The predictive variables (demographics and relevant history, and delivery type) will be captured at the start of the session. The primary outcome variable is likelihood of success (pass/fail) of the MRI simulation, and will be measured at the end of the assessment. Anxiety will also be measured at three time points. Usability testing will be conducted throughout to capture possible quality improvements and amendments to each of the program delivery modes.

Inclusion/Exclusion Criteria

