The predictive success in avoiding sedation will be measured using Motrak® software assessment. MoTrak® uses a sensor attached to the participant's head to determine the position of the head in space relative to a transmitter located within the simulator. The sensor records angular rotations as well as positional displacements from an initially calibrated position. This information is displayed and logged by the program in real-time, allowing objective observation of head motion in an MRI simulator.³² The fail threshold is set at 3mm of movement in any of the positional displacements (x,y,z), which is in accordance with imaging protocols at the Hospital.

Child Anxiety: Venham Picture Test – 5 minutes

Anxiety assessment with children will be completed in pictorial form to better adapt to the cognitive and communicative abilities and styles of younger children. The Venham Picture Test has been well-validated in children for assessing procedural anxiety^{33,34}, and comprises eight cards which two figures on each card, one anxious character and one non-anxious character. The children will be asked to point at the figure they feel most like at that moment. All cards will be shown in their number order. If the child points at the anxious figure, a score of one is recorded and if the child points at the non-anxious character, they will be given a score of zero. Children will complete the at three timepoints (before, during, after the mock MRI).

Secondary Measures

Parental Anxiety: Short State-Trait Anxiety Inventory (Short STAI) – 5 minutes

Anxiety assessment with parents/guardians and children at baseline, after completing the intervention, and before the mock MRI. The Short STAI is a 6-item, adapted version of the well-validated Spielberger State-Trait Anxiety Inventory Scale.³⁵ It distinguishes between general proneness to anxious behavior rooted in the personality and anxiety connected to a current state, and has been validated for use in children.³⁵

Demographics and Relevant History

Demographic and possible confounding information (age, sex, prior experience with medical imaging, experience with virtual reality, type of mobile phone) will be obtained through a data collection form. Data will be de-identified using a participant identification number.

Length of Stay (LoS)

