A priori power analysis was calculated using G-Power.³⁸ A total sample size (N) of 93 was calculated to be needed across the 3 groups (31 per group), with a significance level of 95% ($\alpha=0.05$) and a power of 90% ($\beta=0.10$), allowing for a 10% drop out rate. An effect size of 0.2 was selected to reflect the research suggesting that CLS preparation can reduce sedation rates by 20%.

Descriptive analysis will be conducted on the demographics and relevant history data.

Differences in predictive success of the MRI simulation ranking scores (pass or fail) will be examined using a Repeated Measures ANOVA, within-between interaction for three timepoint measurements (before, during, after) of anxiety and delivery type (VR, mock MRI, booklet). In the case of an off-normal distribution, non-parametric tests may be used. Multivariate analysis will test for possible confounding effects (demographics and relevant history).

Survey data (USE questionnaire, Smileyometer) will be analyzed using means and standard deviations of all respondents for each category of the questionnaires. The proportions of the participants reporting high, medium, or low levels will also be calculated.

Study staff will document responses to the guided survey and read the recorded answers back to participants to verify accuracy and elicit possible further reflection. All of the qualitative data will be uploaded to NVivo by study staff. When complete, study staff will code the information to identify major themes, gaps, barriers within the existing approach and the team will devise recommendations for improving the preparation programs. The phases of this process include:

- Familiarizing yourself with the data

- Generating initial codes
- Searching for themes
- Reviewing themes
- Defining and naming the themes
- Triangulation with other findings and producing a report

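### Age is collected as a possible confounder but has no fixed place in the pass/fail analysis, although allocation is only partly random

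*Combined protocol and SAP*

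**What the plan says.** All of this is in the combined protocol and SAP.

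- **Outcome.** Section 4.4 makes pass or fail on the MRI simulation the primary outcome variable. Failure is 3 mm of head displacement in any direction.
- **Main analysis.** Under Analysis and Interpretation, pass/fail is to be examined by a repeated-measures ANOVA with three anxiety time points and three delivery types. Age is not a term in it.
- **Covariates.** The only sentence on adjustment is "Multivariate analysis will test for possible confounding effects (demographics and relevant history", with the closing bracket following.
- **Collection.** Under Demographics and Relevant History the form records "Demographic and possible confounding information (age, sex, prior experience with medical imaging, experience with virtual reality, type of mobile phone".
- **Allocation.** The plan concedes that full randomisation is not possible; instead "participants will be randomly assigned to the intervention options available according to their individual availability". No stratification by age is described.
- **Why age might matter.** Section 3.0 lists age among many factors in pre-procedural anxiety. It also reports that the hospital requires children under 7 to pass the simulator before a non-sedated scan.
- **Sample size.** "A total sample size (N) of 93 was calculated to be needed across the 3 groups (31 per group"), "allowing for a 10% drop out rate".

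**The concern.** A baseline variable that the plan itself calls a possible confounder should have a fixed role before data are seen. Here a reader cannot tell whether age will be in the model that gives the main result, in what form, or which estimate stands if adjusted and unadjusted results disagree.

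Two things are at stake. The first is bias. If one arm has more young children, and young children pass less often, the raw difference in pass rate moves with the imbalance. Chance can cause this at 31 per arm. Availability-based allocation could also cause it systematically, if the days a family can attend vary with the child's age. The second is precision. A predictive covariate left out of a comparison of this size costs some power. A significance test for confounding in about 90 children would be a weak guard against either.

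**Working it through.** **Inputs from the documents.** 31 per arm; alpha 0.05; ages 4 to 13. Table 2 gives 283/344 = 82% converted to non-sedated MRI. The sample-size paragraph refers to a 20% effect.

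**Assumptions.** The documents give no pass rate by age and no age distribution. I take the better arm at 82% and the comparator at 82 − 20 = 62%; age uniform from 4 up to the 14th birthday; 30% under 7 for the share calculation; and an odds ratio for passing of 1.2 to 1.75 per year of age.

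**The plan's own sample size.** For a repeated-measures ANOVA, within-between interaction, λ = f²·N·m/(1 − ρ). With f = 0.2, m = 3, k = 3 groups and the usual defaults ρ = 0.5 and ε = 1, 90% power needs N = 69 (λ = 0.04 × 69 × 3/0.5 = 16.6). Dropout makes this 69/0.9 = 77, not 93. N = 84 before dropout gives 84 × 1.1 = 92.4, so 93. It arises with ρ of about 0.37 to 0.38, with ε of about 0.75, or with two time points instead of three. Since ρ and ε are not stated, 93 is not reproduced but is not shown to be wrong. The age point does not depend on it.

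**Power for pass/fail.** One pairwise comparison, two-sided 0.05, 31 per arm, logistic likelihood-ratio tests, 4,000 simulated trials per row, marginal rates held at 62% v 82%:

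| Odds ratio per year | Without age | With age | Gain (points) |
|---|---|---|---|
| 1.0 (no effect) | 43% | 43% | 0 |
| 1.2 | 43% | 45% | 2 |
| 1.35 | 44% | 48% | 4 |
| 1.5 | 43% | 50% | 7 |
| 1.75 | 43% | 57% | 14 |

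At 50% v 70% the pattern is the same: 37–38% without age, 40% to 52% with it. For comparison, 90% power at 62% v 82% needs 104 per arm.

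**Chance imbalance in the under-7 share.** A difference of 20 points or more is at least 7 children, since 6/31 = 19.4% and 7/31 = 22.6%. For two independent Binomial(31, 0.3) counts, P(|difference| ≥ 7) = 7.1%. The normal approximation, with SD √(2 × 0.3 × 0.7/31) = 0.116, gives 8.6%; the exact figure is preferable.

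**Chance imbalance in mean age.** SD of age = 10/√12 = 2.89 years. SE of a pairwise difference = 2.89 × √(2/31) = 0.73, so the 95% range is ±1.4 years. By simulation the largest gap across three arms exceeds one year with probability 36%.

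**What imbalance does to the estimate.** A one-year gap in mean age shifts the raw pass rate by about 4 to 9 points over the odds ratios above. For the under-7 share, a log-odds slope of 0.3 per year (odds ratio e^0.3 = 1.35) implies a pass gap of about 30 points between under 7 and 7 or over. A 20-point imbalance then shifts the difference by 0.20 × 30 = 6 points, against a 20-point planned effect.

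**Where age helps.** These gains apply to pass/fail and other between-arm comparisons. In the time-by-delivery interaction, a fixed age term is already absorbed by the subject effect. It adds no power there unless age changes the anxiety trajectory.

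**The case against.** The strongest reply is that the plan does intend to look at covariates. It calls demographics predictive variables, lists age first among possible confounders, and promises a multivariate analysis. A reader might infer a rule under which a significance test decides whether to adjust. The text states no such rule, so the defect is that the role of age is undefined, not that a harmful rule is written down. That part of the reply stands.

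A reader might also infer that age is known to be a strong predictor of passing. The documents do not say so. Section 3.0 lists age unranked among factors in anxiety, not in head motion; the under-7 rule carries no pass rate; and Table 2 is not split by age. Very steep effects are not credible as planning figures. At a log-odds slope of 0.8 per year, passing would run from 6% at age 4 to 99% at age 13. Nor do the documents show that age clusters by day; this is a possibility that the allocation method leaves open.

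Finally, the chance imbalance is modest: about 1 in 14 for a 20-point gap between two arms. And there is no logistic model in the plan to which age could simply be added. Both are true. They limit the size of the gain and widen the fix, but they do not remove the reason for it. If age has no effect, the simulation shows no power lost by including it.

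**Conclusion.** The point holds as a gap in prespecification that is cheap to close. Age is collected and flagged by the plan, and is neither stratified nor fixed in the analysis of the primary outcome, under an allocation that the plan admits is not fully random.

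The likely benefit is moderate: about 2 to 14 points of power for odds ratios of 1.2 to 1.75 per year, with the upper end requiring a truly strong age effect, plus protection against a shift of several points if arms differ in age. All of these figures rest on assumed pass rates and age effects. It would be wrong to conclude that adjustment rescues the design: with age included, power for a 20-point difference stays between about 45% and 57% at 62% v 82%, far from 90%. It should be changed, but it is not the largest weakness of the pass/fail analysis.

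**What to change.** 1. Analyse pass/fail with a logistic model in place of the repeated-measures ANOVA, which does not suit a single binary outcome. Include delivery type and age in years (continuous) in every case, whatever any test of confounding shows.
2. Report the standardised risk difference with its confidence interval for each planned comparison, and state that this adjusted result is the main one.
3. Keep sex, prior imaging, VR experience and phone type for a sensitivity analysis.
4. Log the options open to each child at allocation and adjust for that set, collapsing sparse sets. At 62% v 82% a pairwise comparison has only about 31 × (0.38 + 0.18) = 17 failures, and a set with one open option contributes no within-set comparison. If the primary model becomes unstable, move this adjustment to a sensitivity analysis.
5. If age is also wanted in the anxiety analysis, specify an age-by-time term.

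The cost is slight: revised analysis wording, one extra model term, and a record of the options offered. Age is already on the data collection form, and no change to allocation is required.

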4.5 Phase 3: Economic Evaluation and Impact Modelling

Objective 3: Evaluate costs and benefits of the VR solution and status quo; and conduct economic modelling on the prospective impact of operational integration.

The final phase of this project seeks to answer the following questions:

- What are the current costs of Sedated and Non-Sedated MRI procedures at BC Children's Hospital? (including hospital/health systems costs and average economic burden on patients and families).
- What is the total cost avoidance and opportunity-cost savings in converting a sedated case to a non-sedated case?
- What is the cost-effectiveness of current interventional strategies?
- What is the potential incremental cost-effectiveness ratio of the VR simulation compared to the status quo model (given known limitations)?
- What are the relative impacts to patient/families, hospital, and the health system at large of the various interventions?

The economic modelling will be conducted in a series of stages: (1) cost analysis, (2) outcomes (benefits) analysis, and (3) multi-level modelling of cost-effectiveness (from patient/family, hospital, health systems perspectives).

Stage 1: Cost Analysis

Costs will be analyzed from the perspective of the program implementer (hospital) and estimated for patients/families, and will be reported in Canadian dollars.

For hospital costs, we will analyze administrative/operational costs and clinical volume to present an average case cost for the status quo model and intervention groups. Program costs will be categorized into capital and operational costs, and segmented as technology, administrative, operational and resource costs:

- Technology costs will include hardware devices, technology-related consumables, and technical support. Capital costs for the media development will be measured for the purposes of a parallel return on investment (ROI) analysis, but will be excluded from operational cost-effectiveness analysis (CEA), with the assumption that in many scenarios existing media may be available for use. Multiple CEA models will be produced at varying media costs thresholds, simulating custom content development (using actual incurred/in-kind costs) as well as estimated costs for 'off-the-shelf' media procurement (based on current state market pricing).
- Administrative, Operational and Resources costs will include program management, infrastructure, human resources (e.g. child life specialists, physicians, technologists), medications, associated resources, and consumable supplies.

When presenting the description of the program costs, we will break the components into fixed and variable costs. Fixed costs are defined as not varying, or varying minimally, with the volume of users and variable costs will be tied to the number of users. Fixed costs may include technology, administrative support, staff, and promotional costs. Variable costs may include consumables and medication.

Time-Driven Activity Based Costing (TDABC)

For the analysis of human resources costs, the TDABC methodology will be used to assign costs based on relative resource utilization. TDABC combines business process mapping with detailed assessment of time intervals and resource involvement. The unit cost for each resource will be derived from our review of hospital financial, operational, and clinical volume data (defined as per minute resource costs). Unit costs (per minute estimates) will be multiplied by the relevant time estimate of the activity (or component of), segmented by task and resource.

- The **per minute unit costs** of supplying the capacity will be derived by dividing the total annual costs of individual resources by the minimum annual hours of service. This information will be derived from our review of hospital financial, operational, and clinical volume data.
- **Time estimates** for relevant tasks associated with the programs will be derived from our LoS data and process mapping information gathered in Phase 2

To estimate patient and family costs, multiple scenarios will be defined based on scheduling and administrative data available the Medical Imaging and Child Life Department. No personally identifiable information will be used in any modelling of patient and family costs. Through an analysis of administrative data, we will determine average length of stay for current MRI patients (simulation and actual imaging). Patient/Family costs will be estimated to include opportunity cost (of time spent), travel and accommodation (where applicable – e.g. when simulation and actual imaging are on different dates).

Stage 2: Outcomes (Effects) Analysis

Outcomes will be reported at both the hospital and patient/family perspective, based on the data gathered in Phase 2 (**Table 4**); this includes the predictive non-sedation rates, length of hospital stay, and reductions in anxiety from the patient and family perspectives.

Stage 3: Multi-Level Cost-Effectiveness Modelling

Cost-Effectiveness will be modelled across the various scenarios identified and from multiple perspectives (i.e. hospital, patient/family). To support decision-making, we will determine the **incremental cost-effectiveness ratio (ICER)** of the intervention versus the control. ICER is a statistic used to summarise the cost-effectiveness, and is defined by the difference in cost between two possible interventions, divided by the difference in their effect; this represents the average incremental cost associated with 1 additional unit of the measure of effect. For our study, we will measure ICERS for multiple outcome variables that are measured in Phase 2.

Uncertainty Analysis

We expect the number of users, the average amount of consumables and equipment used, and the amount spent on promotional costs to fluctuate. Therefore, we will conduct a probabilistic uncertainty analysis around these program variables to determine sensitivity and what the expected range of cost-effectiveness might be. These values and distribution for the uncertainty analysis will be selected based on one-year data.

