The issue of pre-procedural anxiety is critically important because it not only impacts patient experience and is associated with psychological and physiological distress, but it can affect the efficiency of medical procedures, length of stay in the hospital (LoS), and resource utilization – all of which have economics impacts to both families and the health

system. During medical imaging procedures specifically, anxiety can cause non-compliance or unintentional movement which often leads to failure to complete the procedure or poor image quality, necessitating multiple attempts or the use of sedation to achieve the desired quality of imaging. The impact of sedating a patient has several downstream effects, including the increased potential for adverse events, as well as the need for specialized clinical staff (i.e. Anesthesiologists, Post-Anesthetic Care Nurses, etc.), medications, and lengthier post-procedural monitoring. Studies have also indicated an increase in negative post-procedural outcomes when patients are sedated, such as increased pain perception, increased pharmaceutical consumption, reductions in sleep and eating, generalized anxiety, and greater dissatisfaction.²⁻⁸

Child Life Magnetic Resonance Imaging (MRI) Simulations

The literature suggests that approximately 50-to-75% of all patients who undergo MRI exams at pediatric hospitals are sedated.⁹ CLS reduce sedation rates by exposing pediatric patients to MRI simulations, thus alleviating symptoms of pre-procedural anxiety and distress. MRI simulations include mock scans that appear and sound identical to the real MRI, but lack the magnet, and thus functionality to take images. It's suggested that preparation programs like this can reduce sedation rates by about 20% (those who are eligible, recruited, and successful).⁹

Between November 2017 and January 2019, approximately 377 of the pediatric patients attending BCCH for MRI were eligible and referred for preparation with a CLS. Of the patients who proceeded with simulation (N=344), 82% were able to successfully be converted to a non-sedated MRI (**Table 2**).

Table 2. Simulation statistics from BC Children's Hospital (BCCH) Child Life Department, Nov2017 – Jan2019.

	Non-Sedated MRI	Sedated MRI
Passed Simulator	283	8
Failed Simulator	0	53
TOTAL	283	61

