It is evident from the literature and our own hospital data that CLS preparation is effective in reducing anxiety, non-compliant behaviors, and sedation rates.⁹ At BCCH, children under the age of 7 who wish to have a non-sedated MRI must pass an MRI simulator with a CLS. However, the patient's ability to prepare with a CLS can be impacted by geographical barriers and socioeconomic status. Transportation barriers have been repeatedly identified in the literature and by parents as a source of unmet health needs for children in both rural and inner-city populations.¹⁰ This is significant, because if a caregiver cannot get their child to the MRI simulation, they miss the opportunity for a non-sedated MRI, and consequently that increases resources and the risk for complications.

How can digital intervention help to improve access?

Given the effectiveness of CLS preparation programs on the success of non-sedated MRI⁹ and the promising evidence that immersive technologies can effectively reduce pre-procedural anxiety and non-compliant behaviors,^{11,12,21,13-20} we sought to make quality improvements and adjustments to the MRI experience by developing and evaluating a multisensory, realistic, and vivid virtual preparation program. Immersive VR experiences create a three-dimensional image that appears to surround the user. Complimented by high visual and sound quality, motion sensors, and speech recognition, VR can take input from users to interact with a highly realistic and vivid virtual environment. As such, our virtual MRI preparation program has the capacity to expose patients to experiences that mimic medical imaging procedures without the financial and physical limitations associated with traditional in-person simulation. Finding effective solutions for patients with geographical barriers and lower socioeconomic status are worthwhile in reducing sedation rates, increasing cost-savings and improving hospital efficiency.

Project Purpose

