- 9) Participants will be informed that they will now be completing a simulation test with the MRI scanner. Participants will be reminded of their free and informed ongoing consent.
- 10) The participant will be transferred to the simulation room, located in the medical imaging center at BCCH. Upon entering the simulation room, participants will verbally complete the VPT with staff (during test). In parallel, parents will complete the Short STAI on the iPad. (5 minutes)
- 11) Participants will be guided through a mock MRI and be assessed using MoTrack®, an objective head motion tracking system.³² The simulation will be completed over 20 minutes and will involve progression through the “MRI procedure”, remaining in the bore for 8 minutes. All participants will receive the same type of simulated scan. We will not be simulating any invasive procedures that can sometimes occur during the MRI (i.e. an IV or intravenous contrast liquid). Please note that this assessment involves a mock procedure using the simulator, not a real MRI.
- 12) Immediately following the simulation, participants will verbally complete the VPT with staff (post-test). In parallel, parents will complete the Short STAI on the iPad. (10 minutes).

- 13) Users will be asked to indicate on the *Smileyometer* how they thought the preparation activity was overall in preparing them for the MRI. Parents/guardians will be asked to complete the USE Questionnaire.
- 14) Staff will ask the user open-ended questions on the preparation materials according to three separate criteria of fun, ease of use, and how good it was for learning about the MRI experience. The final usability assessment will take a total of 10 minutes.
- 15) After the session is "complete", children will be told that they "happen to have some time left" so they can play with any of the preparation materials offered (VR, Mock MRI, Booklet) for 5-minutes if they want to "because they did so well during the activity." This will give children a natural choice selection and will be used to gauge preferences for the activities.
- 16) A verbal session debrief will include an opportunity for questions to mitigate any residual feelings of discomfort or anxiety that may arise from the project's activities.

Outcome Measures

The measures used to evaluate the intended outputs and outcomes associated with this project are outlined below (**Table 4**).

Table 4. Outputs and outcomes associated with the project.

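### The economic model takes simulator pass rates in volunteers aged 4 to 13 as its predictive non-sedation rate, with no step that carries the effect to referred patients and no uncertainty on it

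*Combined protocol and SAP*

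**What the plan says.** Section 4.4 defines the primary measure: "The predictive success in avoiding sedation will be measured using Motrak® software assessment". A child fails on 3 mm of displacement in any axis, and no separate threshold is given by age. The implementation steps are explicit that this is a surrogate: "Please note that this assessment involves a mock procedure using the simulator, not a real MRI".

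On the sample, section 4.4 states: "A minimum of 93 participants (31 participants per group) aged 4-to-13 will be recruited through convenience sampling". Recruitment is open, so that "participants may not be BCCH patients scheduled for an MRI"; resource constraints are given as the reason. Age is recorded as a possible confounder, and the analysis section plans a multivariate test for confounding. It states no estimate by age band and no treatment-by-age term.

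Section 4.5, Stage 2, describes the outcomes taken from Phase 2: "this includes the predictive non-sedation rates, length of hospital stay, and reductions in anxiety from the patient and family perspectives". Stage 3 then forms ICERs on several Phase 2 outcomes. The uncertainty analysis names the number of users, consumables and equipment, and promotional spending. The opening questions of section 4.5 ask what is saved by converting a sedated case. They describe the VR ICER as potential and subject to known limitations.

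The Introduction describes the clinical setting: "children under the age of 7 who wish to have a non-sedated MRI must pass an MRI simulator with a CLS". Of 344 referred patients who went through simulation, "82% were able to successfully be converted to a non-sedated MRI".

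**The concern.** Cost per conversion needs the effect in children who would otherwise be sedated. A volunteer with no MRI booked is not a case that can be converted, and the sample spans ages beyond the group for which the documents state a simulator requirement. If the benefit of preparation differs by age, the all-volunteer difference is an average over the recruited age mix, which need not resemble the mix of Child Life referrals. Adjusting for age as a confounder does not supply the effect in the referred group.

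The ICER has this effect in its denominator, so at a fixed incremental cost any proportional error in the effect passes straight into the ICER. Because the effect is not among the inputs to be varied, the reported range of cost-effectiveness would show neither the mismatch nor the sampling error.

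**Working it through.** **Inputs from the documents.** Table 2: 283 passed and were not sedated, 8 passed and were sedated, 0 failed and were not sedated, 53 failed and were sedated. Phase 2: 93 children, 31 per group, aged 4 to 13.

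**Inputs assumed.** The documents give neither the share *s* of volunteers under 7 nor the ratio *r* of the effect at 7 to 13 to the effect under 7. Even ages across ten years of age give *s* = 3/10 = 0.30; I show 0.10 to 0.70. I show *r* from 0 to 1.

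**1. The plan's own figure.** 283/344 = 82.3%, which agrees with the stated 82%.

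**2. From pass to non-sedation, in referred patients.** 283/(283 + 8) = 283/291 = 97.3%, and all 53 who failed were sedated. A 20-point gain in passes becomes 0.20 × 283/291 = 0.195, a correction of about 3%. A large error cannot come from this link. It would have to come from moving the effect between populations.

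**3. From volunteers to under-7s.** The all-volunteer effect is

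d_all = s × d_under7 + (1 − s) × d_7to13,

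so the factor by which it understates the under-7 effect is 1/[s + (1 − s) × r].

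At *s* = 0.30:
- r = 0: 1/0.30 = 3.33
- r = 0.25: 1/0.475 = 2.11
- r = 0.5: 1/0.65 = 1.54
- r = 1: 1/1 = 1.00

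In points, with an illustrative 20 under 7: 0.3 × 20 + 0.7 × 0 = 6; 0.3 × 20 + 0.7 × 10 = 13; 0.3 × 20 + 0.7 × 20 = 20.

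At *r* = 0 and other age mixes, the factor is 10 at s = 0.10, 5 at 0.20, 2 at 0.50 and 1.43 at 0.70.

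**4. The opposite direction.** Suppose the gain is 0.20 at every age and is credited to all ages, but leads to avoided sedation only under 7. The usable gain at *s* = 0.30 is 0.30 × 0.20 = 0.06, so the benefit is overstated 0.20/0.06 = 3.33-fold. Separately, if older children gained more than the youngest (r above 1), the factor in step 3 would fall below 1.

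**5. Precision.** Take 82% against 62% as an illustration. With 31 per arm, SE = √[(0.82 × 0.18 + 0.62 × 0.38)/31] = 0.111, and the 95% interval is 0.20 ± 1.96 × 0.111, about −0.02 to 0.42. With even ages, 0.30 × 93 ≈ 28 children are under 7, about 9 per arm. Then SE = √(0.3832/9) = 0.206, and the interval is about −0.20 to 0.60. In both cases the ICER denominator can be zero.

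**The case against.** The strongest reply is that the plan is candid. It calls the rates predictive and the ICER potential, says that the scan is simulated, and explains why non-patients are recruited. An ICER per simulated pass is legitimate if labelled as such. That stands as to disclosure. But the caveats change no analysis, and the scenarios described in section 4.5 concern patient and family costs and media costs, not the effect.

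Three stronger readings are tempting and are not supported:

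- **That the ICER is several-fold wrong.** This needs an age mix and an age difference in effect that the documents do not give. The factor can be 1.0, and the direction is open.
- **That only under-7s need the simulator, and that older children pass in any arm.** The Introduction states a requirement for under-7s. It does not say how sedation is decided from age 7 up, and Table 2 gives no ages.
- **That the 8 sedated passers undermine the surrogate.** In Table 2 the link is 97.3%. Those patients were prepared by Child Life Specialists, so whether the figure holds for VR or booklet passers is untested in either direction.

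The choice of contrast also matters. The 20% quoted from the literature is a reduction in sedation rates from preparation programmes, not a difference in pass rates between VR and the status quo. The second hypothesis in section 4.2 expects no difference between VR and mock MRI. If that is true at every age, dilution by age has little bearing on that comparison. It could still matter against the booklet. The ICER section does not say which of the two is the control.

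Finally, basing the ICER on about 9 under-7s per arm would exchange a possible bias for very poor precision. That objection stands and shapes the fix.

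**Conclusion.** The concern holds as a gap between the population studied and the population modelled. The pass rate from volunteers aged 4 to 13 enters the ICER as a predictive non-sedation rate. The economic question concerns sedated cases that could be converted, no step connects the two, and the effect is not among the listed uncertainty inputs.

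The effect per converted case may be materially biased, but neither the size nor the direction is known. The 1.0 to 3.3 range rests on an assumed 30% of volunteers under 7 and on effects from age 7 up that lie between none and equal to those in younger children. The value 1.0 applies when the effect is equal at all ages and is used for under-7s. The documents do not show that the ICER is in fact biased, only that the plan could not reveal it if it were. The step from pass to non-sedation is a minor matter, about 3%.

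**What to change.** - Label the Phase 2 output as simulator pass in volunteers wherever it enters section 4.5.
- Tabulate passes by arm for under 7 and for 7 to 13. Age is already collected.
- Keep the all-volunteer ICER. Beside it, report one with the effect standardised to the age mix of Child Life simulator referrals. Section 4.5 already draws administrative data from Medical Imaging and Child Life, but for costs and length of stay, so the age mix would have to be requested.
- Report both ICERs for each named comparator, booklet and mock MRI.
- Put a distribution on the effect in the probabilistic analysis.
- Use 283/291 only as a sensitivity input, because it comes from patients prepared by Child Life Specialists.

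The cost is one data request, one tabulation and a small modelling step, with no new participants. The drawback is a very wide interval for under-7s (about 9 per arm if ages are even). For that reason the standardised ICER should accompany the all-volunteer one and not replace it.
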